9.1 Data Handling After Cut-off Date

By its nature, data after cut-off may be incomplete and subject to further change and will not be used for summary statistics, statistical analyses, listings or imputations.

Stop dates are not affected by this rule, e.g. a stop date of AEs, which starts prior to the cut-off, but stops after date of cut-off, will not be changed.

These rules will be applied to all analyses performed for the interim analysis for futility and main analysis. For the final analysis no cut-off date will be applied: the analysis will be performed only after all the data have been collected, fully cleaned and the database has been locked.

9.2 Definition of Baseline and Change from Baseline

In general, the last non-missing measurement prior to the first study drug administration will be used as the baseline measurement.

If the assessment time of any pre-dose baseline assessments (as planned per protocol) and/or the time of initial dosing are unknown, but they are known to have been performed on the same day, it will be assumed that it was performed prior to dosing. Unscheduled assessments may be used in the determination of baseline; however, if the time of either the assessment or initial dose is missing, the unscheduled assessment will be considered to have been obtained after study treatment administration.

If a scheduled pre-dose measurement actually occurred post-dose, then the corresponding measurement will be analyzed similar to an unscheduled post-dose measurement.

Absolute and percent changes from baseline are defined as

absolute change = post baseline value – baseline value

percent change = $100 * (\text{post baseline value} - \text{baseline value}) / \text{baseline value}$

9.3 Study Day / Study Treatment Day

Day 1 is the day of start of study treatment, the day before is Day -1 (no Day 0 is defined). Study day / Study treatment day is defined relative to Day 1.

9.4 Definition of Duration and ‘time since’ Variables

If not otherwise specified, duration will be calculated by the difference of start and stop date + 1 (e.g. survival time (days) = date of death – date of first study drug administration + 1).

The time since an event (e.g. time since first diagnosis) will be calculated as reference date minus date of event.

9.5 Conversion Factors

The following conversion factors will be used to convert days into weeks, months or years:

1 week = 7 days, 1 month = 30.4375 days, 1 year = 365.25 days.

If height is recorded in inches, height (cm) = height (in) \times 2.54.

If weight is recorded in pounds, weight (kg) = weight (lb) \div 2.2046.

9.6 Date of last Contact

The date of last contact will be derived for participants not known to have died at the analysis cut-off using the latest complete date prior to or at the data cut-off date among the following:

- All participant assessment dates (blood draws (laboratory, PK), vital signs, performance status, ECG, tumor assessments, quality of life assessments)
- Start and end dates of anti-cancer therapies administered after study treatment discontinuation.
- AE start and end dates
- Concomitant medication/procedures start and end dates
- Last known to be alive date collected on the ‘Survival Follow-up’ eCRF
- Tepotinib and cetuximab administration start and end dates
- Date of discontinuation on disposition eCRF pages (do not use if reason for discontinuation is lost to follow-up)

Only dates associated with actual examinations of the participant reported in the eCRF will be used in the derivation. Dates associated with a technical operation unrelated to participant status such as the date a blood sample was processed will not be used. Assessment dates after the cut-off date will not be applied to derive the last contact date. This rule is to be applied to AE stop dates, too: if an AE started before the cut-off date and ended after the cut-off date, only the complete start date will be used in the derivation of the last date of contact.

9.7 Definition of On-treatment Period

The on-treatment period is defined as the time from the first dose of study treatment day to the last administration day of study treatment + 30 days, or the cut-off date or death or the start day of subsequent anti-cancer drug therapy - 1 day, whichever occurs first.

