### **8.3.1 Time Period and Frequency for Collecting Adverse Event and Serious Adverse Event Information**

- All SAEs will be collected from the signing of the ICF until the Safety Follow-up Visit at the time points specified in the SoA (Section 1.3). Beyond this reporting period, any new unsolicited SAEs that the Investigator spontaneously reports to the Sponsor will be collected and processed.
- All AEs will be collected from the signing of the ICF until the Safety Follow-up Visit at the time points specified in the SoA (Section 1.3).
- All SAEs will be recorded and reported to the Sponsor or designee immediately and under no circumstance will this exceed 24 hours, as indicated in [Appendix 7](#). The Investigator will submit any updated SAE data to the Sponsor within 24 hours of it being available using the same procedure that was used for the initial report.
- Investigators are not obligated to actively solicit AEs or SAEs after the end of study participation. However, if the investigator learns of any SAE, including a death, at any time after a participant has been discharged from the study, and he/she considers the event to be reasonably related to the study intervention or study participation, the Investigator will promptly notify the Sponsor.

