#### 9.4.2 Safety Analyses

All safety analyses will be performed on the Safety Analysis population unless otherwise specified. All analyses will be presented by cohort and dose level, if applicable. The safety analyses will also be done purely descriptively. Further details will be provided in the IAP.

Endpoint	Statistical Analysis Methods
Primary	
Occurrence of DLTs	The number and percentage of participants in the DLT analysis set during the DLT observation period will be tabulated.
Secondary	
Occurrence of Adverse Events (AEs) and treatment-related AEs	
Adverse events will be coded according to the latest available version of the Medical Dictionary for Regulatory Activities version 21.0 or higher. Severity of AEs will be graded using the NCI-CTCAE (v5.0) toxicity grades. Adverse events related to study intervention will be defined as any AE considered as related to tepotinib and/or cetuximab. Missing classifications concerning study intervention relationships will be considered related to the study intervention.
 
Any TEAEs will be summarized, i.e., those events that are emergent during treatment having been absent prior to treatment or worsened relative to the pretreatment state and with onset dates occurring within the first dosing day of study intervention until 30 days after the last dose of study intervention.
 
Following subtypes of TEAEs will be presented in summaries and tables according to System Organ Classes and Preferred Terms:
 
 
• TEAEs
 
• SAEs
 

Endpoint	Statistical Analysis Methods

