15.2 Secondary Endpoints

15.2.1 Adverse Events

Adverse events will be coded according to the Medical Dictionary for Regulatory Activities (MedDRA; latest version at the time of database lock for each analysis will be used and be specified in outputs). Severity of AEs will be graded using the NCI-CTCAE (Version 5.0) toxicity grades.

Relationship with the study treatment components are collected in the “Adverse Events Details” eCRF page. Adverse Events can be related to tepotinib, cetuximab or both. In case the relationship information is missing for a study treatment component, the AE will be considered as related to that component.

Incomplete AE-related dates will be handled as specified in Section [9.8](#).

Treatment emergent adverse events (TEAE) are those events that occurred during on-treatment period, having been absent prior to treatment or worsened relative to the pre-treatment state and with onset dates occurring within the first dosing day of study intervention until 30 days after the last dose of study intervention.

For the Adverse Event that started before the first administration of study treatment, the latest toxicity grade before first dose will be considered as the baseline grade and used to assess whether the AE worsens during the on-treatment period.

Pre-existing conditions continuing on-treatment with grade equal or lower than the baseline grade will not be considered as TEAEs.

All analyses described in Section [15.2.2](#) and [15.2.3](#) will be based on TEAEs if not otherwise specified. The AE listings will include all AEs (whether treatment emergent or not). A flag will be added to indicate if the AE is treatment emergent (i.e. started or worsened between the date of first dose of the study treatment and the date of last dose + 30 days).

Unless otherwise specified, TEAEs will be summarized by number and percentage of participants with the TEAE in the category of interest and sorted by primary System Organ Class (SOC) and Preferred Term (PT) in alphabetic order.

Each participant will be counted only once within each SOC or PT. If a participant experiences more than one AE within a SOC or PT for the same summary period, only the AE with the strongest relationship or the worst severity, as appropriate, will be included in the summaries of relationship and severity.

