15.3.2 Serious Adverse Events

The frequency tables as listed in Section 15.2.2 will be prepared for serious adverse events (SAEs).

The listings of SAEs will also be provided with the relevant information with a flag for SAEs with onset outside of the on-treatment period.

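### SAP 15.2.1 contains two TEAE windows: the definition behind the tables stops at new anti-cancer drug therapy, while the listing flag and the protocol run to last dose + 30 days

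*SAP*

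**What the plan says.** **Protocol 9.4.2** summarises as TEAEs events that are new or worse than before treatment, with onset from the first dosing day "until 30 days after the last dose of study intervention". It does not mention new therapy.

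**SAP 15.2.1** defines TEAEs as "those events that occurred during on-treatment period, having been absent prior to treatment or worsened relative to the pre-treatment state" and, in the same sentence, "with onset dates occurring within the first dosing day of study intervention until 30 days after the last dose of study intervention". It adds that the analyses in 15.2.2 and 15.2.3 "will be based on TEAEs if not otherwise specified". Further on, it says the AE listings cover all events and carry a treatment-emergent flag, explained as "started or worsened between the date of first dose of the study treatment and the date of last dose + 30 days".

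**SAP 9.7** starts the on-treatment period at first dose. It ends the period at the earliest of last administration plus 30 days, the cut-off date, death, or "the start day of subsequent anti-cancer drug therapy - 1 day, whichever occurs first".

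**SAP 15.3.2** lists SAEs "with a flag for SAEs with onset outside of the on-treatment period", which is the truncated period. **SAP 15.3.1** tabulates deaths within 30 days of last dose, without truncation.

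**SAP Section 7**, which is reserved for changes from the protocol, covers only COVID-19.

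**The concern.** One section of the SAP gives two answers to whether an event is treatment-emergent. The tables rest on a definition containing a condition that neither the protocol nor the SAP's own listing flag has. An event in the gap would be flagged in the listing and absent from the summaries of TEAEs, serious TEAEs and TEAEs leading to death.

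The data would exist. Protocol 8.3.1 says: "All AEs will be collected from the signing of the ICF until the Safety Follow-up Visit". Nothing there stops collection when another therapy begins.

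Safety and tolerability of the combination is a secondary objective, and the planned cohorts at the RP2D are 22 and 20 participants. One participant left out of an incidence moves it by 1/22 = 4.5 or 1/20 = 5.0 percentage points. A mismatch between tables and listings, or a departure from the protocol found only at reporting, is easily avoided by settling the text now.

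**Working it through.** The plan states no figure to reproduce. The check compares the windows and then counts days.

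**Step 1. Upper end of each window**

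| Source | Use | Ends at last dose + 30 days | Also ends the day before new drug therapy |
|---|---|---|---|
| Protocol 9.4.2 | TEAE summaries | yes | no |
| SAP 15.2.1 definition, with 9.7 | TEAE tables | yes | yes |
| SAP 15.2.1 flag | AE listings | yes | no |
| SAP 15.3.2 flag, with 9.7 | SAE listing | yes | yes |
| SAP 15.3.1 | 30-day deaths | yes | no |

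The other two stops in 9.7 cause no conflict. Data after cut-off are excluded anyway under SAP 9.1, and no event can start after death.

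**Step 2. How the SAP definition combines its conditions.** The on-treatment requirement and the onset requirement are joined by *and*. Both must hold, so the narrower window governs.

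**Step 3. One event followed through the outputs.** A new AE starts after new anti-cancer drug therapy and within 30 days of last dose.

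- Protocol: TEAE.
- SAP listing flag: treatment-emergent.
- SAP TEAE tables, read literally: not counted.
- If serious: flagged treatment-emergent in the AE listing, but as outside the on-treatment period in the SAE listing.
- If fatal within 30 days of last dose: counted among 30-day deaths, but not among TEAEs leading to death.

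**Step 4. Direction.** Every event that meets both SAP conditions also meets the protocol's condition, so the table count is at most the protocol count.

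**Step 5. Days lost per affected participant.** Count days from last dose, and let new drug therapy start on day d, with d from 1 to 30. The truncated window ends on day d - 1 and the protocol window on day 30.

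Days lost = 30 - (d - 1) = 31 - d.

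| d (assumed) | Days lost |
|---|---|
| 1 | 30 |
| 7 | 24 |
| 14 | 17 |
| 21 | 10 |
| 30 | 1 |
| no new drug therapy by day 30 | 0 |

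The values of d are assumptions, because the documents do not say when subsequent therapy starts.

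**Step 6. Scale.** As a share of the 30 follow-up days, 17 is 57% and 10 is 33%. As a share of the whole TEAE window they are much smaller. Under the protocol's illustrative 5 cycles, treatment lasts 5 × 21 = 105 days and the window is 105 + 30 = 135 days. Then 17/135 = 13% and 10/135 = 7%. Neither set of percentages is a share of events.

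**Step 7. After the fix.** With one window of last dose + 30 days, the days lost are 0 for every d.

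**The case against.** The strongest reply is that SAP 15.2.1 is ambiguous rather than wrong. Its definition ends with the protocol's own 30-day wording, and the later explanation of the flag spells out the same window. No separate table window is set, so a programmer could reasonably apply last dose + 30 days throughout. This stands in part. A reader might infer that the tables will certainly under-report, and the text does not establish that. The literal reading does give the truncated window, though, and leaving the choice to the programmer is itself a reason to settle it.

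A reader might also infer that many events are at stake because participants in this setting stop at progression and soon start another line. The documents give neither the timing nor the frequency of subsequent therapy. Nor are 57% and 33% proportions of TEAEs lost. A participant counts once per SOC or PT, so a repeat of a term already counted may change nothing. Only subsequent drug therapy ends the period; radiotherapy and surgery do not.

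Nor would the events vanish. The AE listings include all AEs, SAEs outside the period are listed with a flag, and deaths are tabulated to 30 and 90 days. The gap is confined to the summary tables. The safety analysis is descriptive, and DLTs have their own 21-day window, so no decision rule depends on the TEAE window.

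Finally, stopping at new therapy is a legitimate way to avoid charging this regimen with the next one's toxicity, and the protocol leaves further safety detail to the SAP. Both points are fair. The defect is that the cut is applied in one place and not in another, and is not declared as a change. The SAP names protocol version 1.0 as its basis, but the amendment tables up to version 2.0 list no change to the TEAE window, so they do not explain the difference.

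**Conclusion.** The inconsistency is real and should be corrected, as a matter of definition. Read literally, SAP 15.2.1 with 9.7 gives the TEAE tables a narrower window than the protocol and the listing flag, and the SAP does not declare it. The effect runs one way: table counts are equal to or below the protocol counts.

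The loss is 31 - d follow-up days for a participant who starts new anti-cancer drug therapy on day d (1 to 30) after last dose, and zero for everyone else. A count changes only if such a participant then has a new or worsened event inside the lost days that is not already counted under the same term. The documents do not support any statement about how many participants or events that will be. The conclusion rests on reading the two conditions in 15.2.1 as both required. The primary efficacy endpoint and the DLT assessment are unaffected.

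**What to change.** 1. In SAP 15.2.1, remove the on-treatment-period condition from the TEAE definition, so that the AE tables and the treatment-emergent flag both use first dose to last dose + 30 days, as in protocol 9.4.2. Reword in the same way the sentence there that judges worsening of pre-existing events over the on-treatment period.
2. In SAP 15.3.2, define the SAE listing flag by the same window.
3. Leave SAP 9.7 as it is. It also governs laboratory, vital signs, ECG, ECOG and concomitant medication outputs, which this point does not concern.
4. If attribution to the next regimen is a worry, add a supplementary TEAE summary cut at the start of new drug therapy.

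Declaring the truncation in SAP Section 7 and aligning all flags to it would also remove the inconsistency. The protocol window is the simpler default, because it needs no departure from the protocol and the data are already collected.

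The cost is a few words in two SAP sections and, if wanted, one extra table. The downside is that some events due to the next therapy will be counted as TEAEs; the supplementary summary shows how many lie after the switch.

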9.8 Imputation of Missing Data

Unless otherwise specified all data will be evaluated as observed, and no imputation method for missing values will be used.

Imputed dates will be used for the calculation of durations.

In all participant data listings, imputed or censored values will be presented, and imputed or censored information will be flagged.

Missing statistics, e.g. when they cannot be calculated, should be presented as “nd”. For example, if n=1, the measure of variability (StDev) cannot be computed and should be presented as “nd”.

Where tables are presented over different time points, the total of missing and non-missing observations at each time-point should reflect the population still in the trial at that time. This does not apply when imputations are made beyond trial withdrawal. For example, if a participant is still in the trial at the time-point but with missing data, they should be counted in the number of missing observations.

The following rules for imputation will be considered:

Disease history

Incomplete dates for disease history (e.g. initial diagnosis date, date of documented, locally advanced, inoperable or metastatic disease diagnosis) will be imputed as follows:

- If the day is missing, it will be imputed to the 15th day of the month.
- If both day and month are missing and the year is prior to the year of the first study treatment, the month and day will be imputed as July 1st.
- If both day and month are missing and the year is same as the year of the first study treatment, the month and day will be imputed as January 1st.
- If the date is completely missing, no imputation will be performed.

Adverse events

Incomplete AE-related dates will be imputed as follows:

- If the AE onset date is missing completely, then the onset date will be replaced by the start of study treatment.

- If only the day part of the AE onset date is missing, but the month and year are equal to the start of study treatment, then the AE onset date will be replaced by the start of study treatment. For example, if the AE onset date is --/JAN/2015, and study treatment start date is 15/JAN/2015, then the imputed AE onset date will be 15/JAN/2015. If the end date or resolution date indicates that the AE has stopped before start of treatment, this date will be used for imputation instead of start of treatment date.
- If both the day and month of the AE onset date are missing but the onset year is equal to the start of study treatment, then the onset date will be replaced by the start of study treatment. For example, if AE onset date is --/---/2014, and study treatment start date is 19/NOV/2014, then the imputed AE onset date will be 19/NOV/2014.
- In all other cases the missing onset day or missing onset month will be replaced by 1.
- Incomplete stop date will be replaced by the last day of the month (if day is missing only), if not resulting in a date later than the date of participant's death. In the latter case the date of death will be used to impute the incomplete stop date.
- In all other cases the incomplete stop date will not be imputed. If stop date of AE is after date of cut-off this date will be kept.

Previous and concomitant medication/procedure

For identification of previous or concomitant medications/procedures, no formal imputation will be performed on missing or incomplete dates. Rules presented in [Table 2](#) and [Table 3](#) will be used to define if a medication/procedure is considered as a previous, concomitant or both previous and concomitant medication/procedure.

Table 2 Stopping rules for medication/procedure end dates

End date of medication/procedure			Stopping rule		
Day	Month	Year			
UNK	UNK	UNK	After treatment start (ongoing)		
UNK	UNK	< Treatment start (year)	Before treatment start		
UNK	UNK	\geq Treatment start (year)	After treatment start		
UNK	< Treatment start (month and year)		Before treatment start		
UNK	\geq Treatment start (month and year)		After treatment start		
< Treatment start (complete date)			Before treatment start		
\geq Treatment start (complete date)			After treatment start		

UNK = Unknown

Table 3 Rules to define previous and/or concomitant medication

Start date of medication/procedure			Stopping rule (see Table 2)	Medication/procedure		
Day	Month	Year				
UNK	UNK	UNK	Before treatment start	Previous		
UNK	UNK	UNK	After treatment start	Previous and concomitant		
UNK	UNK	<= Treatment start (year)	Before treatment start	Previous		
UNK	UNK	<= Treatment start (year)	After treatment start	Previous and concomitant		
UNK	UNK	> Treatment start (year) and <= Treatment end + 30 days (year)	After treatment start	Concomitant		
UNK	<= Treatment start (month and year)		Before treatment start	Previous		
UNK	<= Treatment start (month and year)		After treatment start	Previous and concomitant		
UNK	> Treatment start (month and year) and <= Treatment end + 30 days (month and year)		After treatment start	Concomitant		
<= Treatment start (date)			Before treatment start	Previous		
<= Treatment start (date)			After treatment start	Previous and concomitant		
> Treatment start (date) and <= Treatment end + 30 days (date)			After treatment start	Concomitant		

UNK = Unknown

Dates of study treatment

Start date of study treatments:

- No imputation will be done.

End date of study treatments:

- In case the last date of study drug is missing or incomplete the date of last administration of study drug will be taken from the treatment termination eCRF pages.
- If the last date of study drug is completely missing and there is no End of Treatment eCRF page and no death date the participant should be considered to be ongoing and use the cut-off date for the analysis as the last dosing date
- If the last date of study drug is completely or partially missing and there is EITHER an End of Treatment eCRF page OR a death date available (within the cut-off date) then imputed last dose date is:
 - 31DECYYYY, if only Year is available and Year < Year of min (EOT date, death date)

- Last day of the month, if both Year and Month are available and Year = Year of min (EOT date, death date) and Month < the month of min (EOT date, death date)
- min (EOT date, death date), for all other case

Death date

In general, missing or partial death dates will not be imputed. However, for the purpose of survival analyses, partially missing death dates will be imputed as follows: if only the day is missing, the death date will be imputed to the maximum of the (non-imputed) day after the date of last contact (see Section 9.6) and the 15th day of the month.

Tumor assessments

All investigation dates (e.g. X-ray, CT scan) must be completed with day, month and year.

If there are multiple scan dates associated with an evaluation, i.e., radiological assessments occur over a series of days rather than the same day, the choice of date of assessment could impact the date of progression and/or date of response. If there are multiple scan dates associated with an evaluation, the earliest of the scan dates associated with the evaluation will be used as the date of assessment.

If one or more investigation dates for an evaluation are incomplete but other investigation dates are available, the incomplete date(s) are not considered for calculation of the assessment date and assessment date is calculated as the earliest of all investigation dates (e.g. X-ray, CT-scan).

If all measurement dates for an evaluation have no day recorded, the 1st of the month is used.

If the month is not completed, for any of the investigations for an evaluation, the respective assessment will be considered to be at the date which is exactly between the previous and the following assessment. If both a previous and following assessments are not available, this assessment will not be used for any calculations.

Dates of subsequent anti-cancer therapy

Incomplete dates for start date of subsequent anti-cancer therapy (drug therapy, radiation, surgery) will be imputed as follows and will be used for determining censoring dates for efficacy related sensitivity analyses:

- If only day is missing, it will be imputed as the first day of the month unless it results in a date before the end date of study treatment. In that case, the incomplete anti-cancer therapy start date will be imputed as the end date of study treatment
- If both day and month are missing, the incomplete anti-cancer therapy start date will be imputed as the end date of study treatment if the subsequent therapy started on the same year as the end of study treatment; otherwise day and month will be imputed as the 1st of January.

Incomplete subsequent anti-cancer therapy stop dates will not be imputed.

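### SAP 9.8 applies its pre-dose stop-date exception to only one of three AE onset rules, so an event known to have ended before dosing can be given a Day 1 onset and flagged as treatment-emergent

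*SAP*

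**What the plan says.** The adverse event part of SAP 9.8 lists these onset rules in order.

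- **Onset completely missing.** "If the AE onset date is missing completely, then the onset date will be replaced by the start of study treatment". Nothing is said about the stop date.
- **Day missing.** "If only the day part of the AE onset date is missing, but the month and year are equal to the start of study treatment", the onset becomes the start of treatment. The last sentence of this bullet adds the exception: "If the end date or resolution date indicates that the AE has stopped before start of treatment, this date will be used for imputation" in place of the treatment start date.
- **Day and month missing.** If both are "missing but the onset year is equal to the start of study treatment, then the onset date will be replaced by the start" of treatment. Nothing is said about the stop date.
- **Everything else.** "In all other cases the missing onset day or missing onset month will be replaced by 1".

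SAP 15.2.1 sends incomplete AE dates to these rules. Its TEAE definition has three elements: the event occurred in the on-treatment period; it was not present before treatment, or it got worse; and it falls in the window "with onset dates occurring within the first dosing day of study intervention until 30 days after the last dose". The flag described for the AE listings is shorter. It marks an event that began or worsened between first dose and last dose plus 30 days.

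Protocol 8.3.1 states: "All AEs will be collected from the signing of the ICF until the Safety Follow-up Visit". Screening lasts up to 56 days (Protocol 1.1 and 4.1), so events that began and ended before dosing can be in the database.

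**The concern.** Setting an unknown onset to the first dose is a sensible conservative choice when the timing really is unknown. A recorded stop date before the first dose removes that uncertainty, because the event was over before exposure. The second bullet accepts this and the first and third do not. As a result, the stop date is ignored in exactly the two cases where the onset is least well known.

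The SAP treats medications differently. Tables 2 and 3 of the same section test the end date at every level of missing start date, and a medication with a wholly unknown start and an end before treatment is classed as previous only. A drug given for a screening event would then be previous, while the event itself, with the same missing start and a known stop, would be imputed to Day 1.

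What is at stake is the TEAE tables of a single-arm study with about 20 participants per cohort. One misplaced event can be visible there, and two programmers working from the same text could reach different counts.

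**Working it through.** **Inputs**

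- Onset rules: SAP 9.8, as above.
- TEAE window and listing flag: SAP 15.2.1.
- Duration = stop − start + 1: SAP 9.4.
- Screening of up to 56 days: Protocol 1.1 and 4.1.
- Planned numbers at the RP2D, 22 (Cohort A) and 20 (Cohort B): Protocol 9.2.
- Assumed, because the documents give no such case: the AE has a recorded stop date of 05 Nov 2014.

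**Step 1: reproduce the SAP's own examples.** For the day-missing rule, onset in January 2015 with treatment start 15 Jan 2015 gives 15 Jan 2015, as the SAP states. For the day-and-month-missing rule, onset in 2014 with treatment start 19 Nov 2014 gives 19 Nov 2014, which agrees with the SAP: "then the imputed AE onset date will be 19/NOV/2014". Neither example includes a stop date, so neither shows how the exception is meant to work.

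**Step 2: check that the case can occur.** 19 Nov 2014 − 56 days = 24 Sep 2014. A stop on 05 Nov 2014 lies inside that screening window.

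**Step 3: apply each rule literally**, with treatment start 19 Nov 2014 and stop 05 Nov 2014.

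| Onset recorded | Imputed onset | Duration (days) | Onset on or after first dose |
|---|---|---|---|
| Completely missing | 19 Nov 2014 | −14 + 1 = −13 | Yes |
| Day missing (Nov 2014) | 05 Nov 2014 | 0 + 1 = 1 | No |
| Day and month missing (2014) | 19 Nov 2014 | −14 + 1 = −13 | Yes |

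The residual rule does not rescue the first and third rows, because it applies only to cases that the earlier bullets leave open. One event with one stop date therefore gets two different onsets, depending only on how much of the onset date is missing.

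**Step 4: carry this to the flag.** In the first and third rows the imputed start lies in the flag's window, and SAP 15.2.1 contains no check of the stop date.

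**Step 5: size.** SAP 15.2.1 counts a participant once per SOC or PT.

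- Cohort A: 1/22 = 4.5 points at most in one row.
- Cohort B: 1/20 = 5.0 points at most in one row.
- If the participant already has another TEAE that counts in that row: 0.

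**Step 6: apply the exception to all three rules.** Every row of the table becomes onset 05 Nov 2014, duration 1 day, not treatment-emergent.

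**The case against.** The strongest reply is that the TEAE definition already excludes these events. It requires occurrence in the on-treatment period, which SAP 9.7 starts at first dose, and it requires that the event was not present before treatment or that it worsened. An event with a recorded pre-dose stop meets neither requirement, whatever its imputed onset. This stands in part: a programmer who applies the full definition to the stop date could leave the event out. But the listing flag is written on start or worsening alone, and the imputed onset contradicts the recorded stop. The text therefore supports both outcomes. A reader might infer that these events will certainly enter the TEAE tables; the documents do not go that far.

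Four further replies deserve weight.

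- **The exception may have been meant for all three bullets.** Nothing in its wording limits it to a missing day. Its position inside one bullet does, and no other text extends it.
- **The trigger is narrow.** The onset month must be unknown although the event arose in a short, observed screening period, and the stop must be known to precede dosing. SAP 6 plans a data review meeting before any database lock, and SAP 9.8 flags imputed values in listings, so such a record may be noticed. This makes the case rare; it does not correct the rule.
- **The effect is often nil.** Protocol 2.3 reports that all participants given tepotinib with gefitinib had TEAEs. If that holds here, the any-TEAE row would not move. A reader might take 4.5 or 5.0 points as the effect of each affected participant, but it is only the maximum for one row.
- **The negative duration reaches no planned table.** The AE analyses in SAP 15 specify frequencies, grades and listings, not durations. The −13 days is a sign of the inconsistency, not a result that would be reported.

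A reader might also infer that the related-event rows are inflated, because SAP 15.2.1 treats a missing relationship as related. That needs a second missing field on the same record and adds no evidence on this point.

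**Conclusion.** The rule is wrong as written, and the point is minor. For an onset that is completely missing, or known only to the year of treatment start, SAP 9.8 ignores a recorded stop date and places the onset after the event ended. Under the listing flag in SAP 15.2.1 the event could then be counted as treatment-emergent, despite the definition's requirement that it be new or worse on treatment.

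Per affected participant, one SOC or PT row moves by between 0 and 4.5 points in Cohort A, or between 0 and 5.0 points in Cohort B. These ceilings assume that the planned 22 and 20 participants are reached and shown at one dose level; a smaller column would give a larger share. The documents give no count of incomplete onset dates, so the total effect cannot be estimated. It is probably small. Objective response, the sample size and the futility rule do not depend on AE dates and are unaffected.

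**What to change.** Take the stop-date sentence out of the day-missing bullet and place it above all three as a general condition:

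- First apply the stop-date imputation already in SAP 9.8.
- If a complete stop date, or a day-missing stop date whose month precedes the month of treatment start, shows that the AE ended before the start of study treatment, set the onset to the stop date.
- Do not flag that AE as treatment-emergent. State this in SAP 15.2.1 as well, so that the flag and the definition agree.

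The month condition is needed because SAP 9.8 moves a day-missing stop date to the end of its month. A stop known only to fall in the month of treatment start does not show that the event ended before dosing.

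The cost is one sentence moved, one short clause added and a trivial programming change, with no new data collection. It should be done before database lock.
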